1. MILD TO MODERATE DISTRESS

- a. If the participant reports mild to moderate stress (but no suicidal thoughts or morbid ideations such as thoughts of wanting to be dead), the participant will be provided a listing of community resources and encouraged to seek help.
- b. Counselor will help the participant develop an action plan to be seen by a mental health professional should their distress persist over multiple sessions or worsen.
- c. Counselor will document the conversation and support materials provided.
- d. Continued distress without professional assistance and support can be a reason to temporarily or permanently withdraw the participant from the *Fit Blue* Weight Loss Intervention protocol.

2. SEVERE DISTRESS AND SUICIDE IDEATIONS WITH NO INTENT OR PLAN Participant reports suicidal thoughts but no intent or plan.

a. Counselor will develop an action plan to get help from a mental health professional. This conversation with the participant and the action plan will be documented.

b. Counselor will follow-up in two business days to ensure that the participant has an appointment with mental health scheduled.

c. Counselor will also inform the participant that if their condition worsens the following emergency resources are available:

1) Mental Health Clinic (open for Walk-Ins during duty hours: [contact])

2) SAMMC ED: [contact]

3) Crisis Hotline call: [name]

3. SEVERE DISTRESS AND SUICIDAL IDEATION WITH INTENT OR PLAN

a. Participant reports suicidal thoughts and intent or plan.

b. Once a participant endorses suicidal intent they are not to be left alone.

c. Whether the Counselor – Participant contact is by phone or in-person, the Counselor will attempt to maintain contact with the participant, identify the location of the Participant and maintain verbal contact until help arrives.

d. Counselor will contact another staff member and indicate they have an emergency and direct them to call 911 (Lackland Command Post: [contact]; Security Forces: [contact]; Ambulance: [contact]) and provide an address.

e. Counselor will document the conversation with the prospective participant and all actions taken.

4.9.1. Minimizing Risks:

This study follows evidence-based lifestyle recommendations for weight loss and improving health, including diet change and regular exercise. If followed according to program guidelines, no adverse medical conditions are expected to result from the research activities.

There are no major risks associated with taking measurements (i.e. height, weight, blood pressure, and waist circumference), taking a health history or collecting questionnaire data. There is, however, the potential risk of loss of confidentiality. Every effort will be made to keep participant information confidential as described in Section 4.8. In the event that questions asked make participants feel uncomfortable, they may refuse to answer and may take a break at any time during a study visit. However, we are not collecting any information that would in any way jeopardize participants' careers in the Air Force.

Being a part of this study while pregnant may expose the unborn child to significant risks. Therefore, pregnant women will be excluded from the study. Women who are able to become pregnant will be asked if they are pregnant at enrollment and each follow-up visit. Women who become pregnant during the course of the study will be withdrawn from the study and referred to their doctor for medical care. Women may breast feed while participating in this study so long as they have continuously breast fed for at least six months postpartum prior to entering the study.

The research may involve risks to the subject (or to the embryo or fetus, if the subject is or may become pregnant), which are currently unforeseeable.

Any significant new findings developed during the course of this research project, which may impact upon the safety and efficacy of the procedure or treatment under study and consequently influence participants' willingness to continue participation, will be provided to them.

4.9.2. Vulnerable Populations: N/A

4.9.3. Clinical Care:

As all participants will be active duty military members, medical care (if needed) is provided at no cost through their Military Treatment Facility (MTF).

4.9.4. Injury Compensation: N/A

4.9.5. Data Safety Monitoring:

The trial will be conducted in compliance with this protocol, International Conference on Harmonization (ICH) Guidelines for Good Clinical Practice (GCP), and any applicable national and international regulatory requirements. The principal and associate investigators will be monitoring all aspects of the study in accordance with the appropriate regulations in order to:

1) Ensure protection of study subjects, compliance with the protocol, and accuracy and completeness of records.

2) Verify the prompt reporting of all data points, including reporting Serious Adverse Events (SAEs) and checking availability of signed informed consent,

The principal investigator will be responsible for the protocol safety monitoring. The PI will make study documents readily available for inspection by the local IRB and over sight staff for confirmation of the study data.

Note: A Data Safety Monitoring Plan (DSMP) has been developed for this study (see attached).

5.0. Alternatives:

Alternatives include not participating in the study, consulting with their Primary Care Provider (PCP) or Health and Wellness Center dietary/exercise experts to assist them with weight loss efforts, joining a private weight loss program not affiliated with the military, or self-monitoring of dietary intake and physical activity to achieve weight loss. Meal replacements may also be bought at local stores.

6.0. Data Analysis:

We will analyze changes in BMI and abdominal circumference, as well as data pertaining to dietary intake and physical activity from baseline, 4-month follow-up, and 12-month follow-up.

6.1. Outcome Measures:

The primary outcome is percentage of weight loss. Secondary outcomes are abdominal circumference, BMI, and self-reported dietary intake and physical activity. Dietary intake will be measured by the Multifactor Screener and the Beverage Intake Questionnaire (BEVQ-15) and physical activity will be measures by the Global Physical Activity Questionnaire (GPAQ). Attitudes and behaviors associated with weighing, dietary behaviors, sleep, and weight loss will be measured using descriptive questions.

Participants will be monitored for excessive weight loss (> 12 pounds per month) and a DSMP has been established that outlines plans for monitoring adverse events and excessive drop-outs.

6.2. Sample size estimation/power analysis:

The study aims to enroll 248 participants, 124 participants in each group. This distribution will provide a diverse representation within each intervention group and will provide the necessary information for data and power analysis.

6.3. Statistical Analysis:

The primary data analysis will adhere to the intention-to-treat principle and in the final analysis, the participants will be categorized according to their initial randomization. We will be using the baseline weight as a covariate in the final primary model where we compare the two arms in terms of the percentage of weight loss. We also plan to carry out secondary analyses where we will investigate the efficacy of the intervention in subgroups of Airmen based on gender, race, and years of service in the Armed Forces. We will also evaluate the impact of adherence on outcome, whether it is number of intervention sessions completed, or adherence to dietary intake and physical activity recommendations. Finally, we'll determine the prevalence of Adverse Events and Serious Adverse Events in the two treatment conditions.

6.4 Number of Subjects:

Number of subjects planned for WHASC	Enrolled in full study	248	to result in	248	completing the full study.
TOTAL NUMBER OF SUBJECTS (nation-wide/study-wide):248					

7. Duration of Study: Approximate duration of the study: 54 months

8. Local and External Support Services:

A letter of support from the 559th Medical Group Commander (559 MDG/CC) is attached. The Health and Wellness Center on Lackland AFB will also provide work space for three study staff members as well as for participant visits/follow ups.

9. Intramural (GME) and Extramural Funding Support:

The National Institute of Diabetes and Digestive and Kidney Diseases provided extramural funding for this study.

10. Conflict of Interest:

If you or any investigator participating in the repository has, or anticipates having, any income from or financial interest in: the sponsor of the repository protocol, the supporting organization, or the company that owns/licenses the technology being studied, contact the WHASC IRB. A "Conflict of interest exists if an employee's position or authority may be used to influence or make decisions that lead to any form of financial or personal gain for that employee or for his or her family which includes spouse or dependent children." [NOTE: A conflict of interest or even the appearance of conflict calls into question the judgment or actions of the investigator in areas that affect the rights and welfare of research subjects and the integrity of the research process. At its worst, conflict of interest may endanger lives, e.g., not only those of the immediate research subjects under study, but those of future patients treated on the basis of biased research results.]

- a. Financial Conflict of Interest: None
- b. Personal Conflict of Interest: None
- c. Current Off-Duty Employment: None

11. Use of an Investigational New Drug, use of a Drug for a non-FDA approved purpose, use of an investigative device or use of a placebo:

This research uses an Investigational New Drug	[] YES [x] NO
This research uses a FDA approved drug for a non-FDA approved purpose	[] YES [x] NO
This research uses an Investigational Device	[] YES [x] NO
This research uses a placebo.	[] YES [x] NO

[] Analytical Chemistry	[] Anatomy	[] Anesthesiology	[] Biochemistry		
[] Cardiovascular Surgery	[] Cardiology	[] Cell Biology	[] Dentistry		
[] Dermatology	[] Dietetics	[] Electrophysiology	[] Endocrinology		
[] Emergency medicine	[] Gastroenterology	[] General Surgery	[] Hematology		
[] Histology	[] Immunology/Allergy	[] Infectious Disease	[] Microbiology		
[] Molecular Biology	[] Neonatology	[] Neurology	[] Neurosurgery		
[] Nursing	[] OB/GYN	[] Occupational Medicine	[] Occupational Therapy		
[] Oncology	[] Ophthalmology	[] Oral/Maxillofacial Surgery	[] Orthopedics		
[] Pathology	[] Pediatrics	[] Pharmacology	[] Physical Therapy		
[] Mental Health	 [] Radiology/Imaging 	[] Urology	[x] Wellness		
[x] Other (state): Prevention, Behavioral					

12. Medical Research Area for the Study: (Pick as many as appropriate)

13. Attachments:

- 1. Certificates of Compliance
- 2. Informed Consent Document
- 3. HIPAA Authorization Document
- 4. Letter of Support 559 MDG/CC
- 5. Letter of Support- HAWC
- 6. Extramural Funding Support Document
- 7. Medical Clearance Letter
- 8. Phone pre-screen form
- 9. Screening Visit Interview Questions form
- 10. Baseline Visit Interview Questions form
- 11. Contact information form
- 12. Demographics form
- 13. Physical Assessment Form (screening, baseline & follow-up visits)
- 14. Global Physical Activity Questionnaire (GPAQ)
- 15. Behavioral Questionnaire
- 16. Health Utility Index/Quality of Life questionnaire
- 17. Brief Beverage Intake Questionnaire (BEVQ-15)
- 18. Multifactor Screener
- 19. Program Evaluation
- 20. Counselor-initiated Program Participant Lessons
- 21. Self-paced Program Participant Lessons
- 22. Recruitment flyer/poster design
- 23. Recruitment electronic/newspaper advertisement
- 24. Recruitment business card
- 25. Data Safety Monitoring Plan (DSMP)

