At the in-person screening visit, a civilian research staff member will review the consent document with the study candidate, allow time for the individual to read the document and ask any questions. If the individual wishes to review the consent with their family or physician, they will be allowed the time to do so and will be re-scheduled to complete the screening visit once they are ready to sign the consent form. If the individual wants to volunteer, they will be asked to sign the consent document and the HIPAA Authorization document. Another civilian member of the research team will witness the consent. Once informed consent is obtained, the research staff will confirm eligibility by collecting demographic information, physical measurements (i.e. height, weight), an array of screening visit questionnaires (see Section 3.6.2), and contact information. A 1-2 week run-in will be explained (see section 3.6.2) and the participant will receive additional instructions that must be completed in order to be included in the study (i.e. obtain military medical clearance, participate in 1 week of dietary and physical activity self-monitoring). The screening visit will take approximately 60 minutes.

The participant will return for the baseline visit in approximately 1-2 weeks at the HAWC. At this visit, run-in material will be reviewed for completeness, physical measurements will be taken (i.e. weight, abdominal circumference, blood pressure and heart rate), and the participant will be randomly placed into one of the two treatment groups. The abdominal circumference measurement will be assessed using the criteria stated in AFI 36-2905, "Fitness Program," Section 7. At this time, research staff will also inquire into current adverse events, such as physical injuries, illnesses or hospitalizations. Fifty percent of participants will be randomly assigned, using a computerized block design unique to the Filemaker v12 relational database application, to the more structured counselor-initiated weight loss intervention and 50% to the self-paced weight loss intervention. If the participant is assigned to the counselor-initiated group, he/she will be oriented to the group and study website, provided lesson materials, exercise guidelines, an electronic body scale, meal replacements, and measuring cups and spoons. If the participant is assigned to

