- Physical Activity Goals: Taking into account the amount of physical activity for each participant at the beginning of the program, participants will be asked to gradually increase their cardiorespiratory (aerobic) exercise > 5 days per week at a moderate to vigorous intensity level (each bout lasting a minimum of 10 minutes), until they reach a total of 225-250 minutes per week. Upon reaching the physical activity goal of 225-250 minutes per week, they will be encouraged to maintain this level of physical activity.

3.6.2. Data Collection and Processing:

Pre-screening (via phone):

- Description of the research project
- Determine eligibility
- Collect name and contact number with oral approval by potential participants
- Schedule in-person screening visit
- Screening visit (in-person):
 - Confirm eligibility
 - Measure weight and height
 - Obtain informed consent
 - Collect demographic information
 - Collect contact information
 - Quality of Life questionnaire (administered by study personnel)
 - Complete brief dietary, physical activity, and weight-related attitudes and behavior questionnaires
 - Explain the 1 to 2 week run-in: The run-in consists of two components: one week of dietary and physical activity self-monitoring and obtaining a letter from their AF healthcare provider approving participation in the intervention (by visiting their healthcare provider or utilizing MiCare, the Air Force's secure patient portal)
 - Participants will use the Lose It! web/mobile based app to collect their diet and physical activity information. Participants will be asked to provide a valid personal e-mail address to access and use Lose It!. If they do not have one or do not wish to use their current personal email address, study staff will assist them in creating a new account for the purpose of

accessing Lose It!. Materials and instruction on using Lose It! will be provided to the participants.

Baseline visit (in-person, 1-2 weeks after screening visit):

- Determine whether run-in requirements were completed
- Measure weight, abdominal circumference, resting blood pressure and resting heart rate
- Randomize participant: If all of the above are completed satisfactorily, participants will be randomized to either the Counselor-initiated intervention group or the Self-paced intervention group.
- Orientation to group assignment and study website

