- 11. Presence of unstable, emotional or psychiatric condition (depression; schizophrenia)
- 12. Severe bronchitis or emphysema that precludes exercise
- 13. History of bariatric surgery or history of significant recent weight loss (> 10 pounds in the past 3 months)
- 14. Scheduled extended leave away from the San Antonio area in the next 13 months (i.e. planned PCS/Deployment/extended TDY greater than 30 days)
- 15. No computer access for self-monitoring using Lose It! and for email feedback from counselor
- 16. More than one failure of the military-proctored physical fitness test in the last 12 months based on AFI 36-2905 (3 Aug 2010), "Fitness Program."
- 17. A military member of the same household is already a FIT Blue study participant
- 18. Any medical condition or medication that could increase or decrease weight loss that might result from the proposed intervention protocol
- 19. Any other medical, psychiatric, or behavioral factors that in the judgment of the screening physician may interfere with study participation or the ability to follow the intervention protocol

3.6.8. Instrumentation:

Phone screen form (during Pre-screening phone call) – Includes name and contact number for scheduling screening visit and eligibility criteria

Screening Visit Interview Questions form (at preliminary screening visit) – aimed at learning about subject's thoughts/feelings concerning weight loss, how much weight they'd like to lose, and readiness for weight loss

Baseline Visit Interview Questions form (at baseline visit) – aimed at learning about subject's thoughts/feelings concerning aspects of their participation thus far

Contact information form (at screening visit) - used to collect and update pertinent contact information

Demographics form (at screening visit) – used to collect pertinent demographic data

Physical Assessment Form (at screening, baseline and follow-up visits) – used to capture weight, height, abdominal circumference, heart rate and blood pressure

Global Physical Activity Questionnaire (GPAQ) (at screening and follow-up visits) – will capture current levels of physical activity of various types and the amount of sedentary behavior

Behavioral Questionnaire (at screening and follow-up visits) – includes descriptive questions related to attitudes and behaviors associated with weighing, dietary behaviors, sleep, and weight loss

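### The primary model names baseline weight as its only covariate; adding gender and years of service in advance would be a cheap, modest improvement, not the repair of an error

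*Combined protocol and SAP*

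**What the plan says.** Section 6.1: "The primary outcome is percentage of weight loss".

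Section 6.3, on the intention-to-treat comparison: "We will be using the baseline weight as a covariate in the final primary model where we compare the two arms". No second covariate is named, though the sentence does not exclude one. The same section plans secondary analyses of efficacy in "subgroups of Airmen based on gender, race, and years of service in the Armed Forces". Those three factors have no stated role in the primary model.

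Section 3.6 allocates participants equally "using a computerized block design unique to the Filemaker v12 relational database application" and names no stratification factor.

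On timing, section 3.6.8 has a demographics form at the screening visit, "used to collect pertinent demographic data". Section 3.6.2 places randomisation at the baseline visit, one to two weeks later. The items on the form are not listed.

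Section 6.2: "The study aims to enroll 248 participants, 124 participants in each group". It gives no alpha, power, effect size or standard deviation.

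**The concern.** The outcome is already expressed relative to starting weight, so the one covariate named may explain little of what remains; the documents give no figure either way. If gender or years of service does predict percentage weight loss, that variation stays in the error term and widens the interval for the primary comparison. Without stratification, a chance difference between arms in such a factor is also left to the model, which does not include it. A noticeable gender imbalance would then invite an adjusted analysis devised after the data are seen.

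Gender has one further link to the outcome data. Sections 4.6 and 4.9.1 withdraw women who become pregnant, so one route to a missing outcome is open to one gender only, and 6.3 states no method for missing data. An analysis of observed outcomes guards against missingness that depends on a covariate only if that covariate is in the model.

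**Working it through.** **The plan's own figure.** 2 × 124 = 248, which agrees with section 6.2. Beyond that the sample size cannot be reproduced, because its inputs are not stated.

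**Assumptions.** Two-sided alpha 0.05, 80% power unadjusted, complete data (section 6.4 expects all 248 to complete). The detectable difference at 124 per arm is (1.960 + 0.842) × √(2/124) = 0.356 SD by the normal approximation. With the noncentral t it is 0.357 SD, where unadjusted power is 79.96%.

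**Effect of adding gender and linear years of service.** Intercept, arm and weight leave 248 − 3 = 245 residual degrees of freedom; two more covariates leave 243. With R² the share of remaining variance that they explain:

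- variance factor = (1 − R²) × 245/243, where 245/243 = 1.0082
- equivalent sample size = 248 / variance factor
- power from the noncentral t at 0.357 SD

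| Assumed partial R² | Variance factor | Equivalent n | Power | Change in points |
|---|---|---|---|---|
| 0% | 1.008 | 246 | 79.6% | −0.3 |
| 2% | 0.988 | 251 | 80.4% | +0.5 |
| 5% | 0.958 | 259 | 81.6% | +1.7 |
| 10% | 0.907 | 273 | 83.6% | +3.7 |

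Measured from a round 80%, the loss in the first row is 0.4 points. Break-even: R² = 1 − 243/245 = 0.8%.

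**What gender alone might be worth.** A simulation (6,000 runs, assumed outcome SD of 6 points, gender correlated with weight) gave these mean standard errors without and with gender in the model:

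- 2-point gender gap: 0.770 and 0.764. Equivalent n = 248 × (0.770/0.764)² = 252, or 4 extra participants.
- 3-point gender gap: 0.779 and 0.764. Equivalent n = 248 × (0.779/0.764)² = 258, or 10 extra participants.

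Type I error was 5.0% to 5.4% with and without gender, so both models are valid. Neither gap reaches the 10% row; that row would need years of service to be strongly prognostic as well.

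**Chance imbalance.** The SD of the difference between arms in the share of women is √(2p(1 − p)/124).

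- p = 0.3: SD 0.058; 0.10/0.058 = 1.72; probability of a gap above 10 points 8.6%.
- p = 0.5: SD 0.064; 0.10/0.0635 = 1.57; probability 11.5%.

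With a 2-point gender gap in percentage weight loss, a 10-point imbalance moves an estimate not adjusted for gender by 0.10 × 2 = 0.2 points, or 0.2/0.77 = 0.26 standard errors. Baseline weight would absorb part of this where weight and gender are correlated.

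**The case against.** The strongest reply is that nothing here is wrong. A randomised comparison adjusted for baseline weight is valid, its confidence interval already allows for chance imbalance, and the gains shown rest on an R² that no document supplies. On the plausible gender scenarios they are small. All of that stands.

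Three stronger readings are tempting, and the documents support none of them.

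- A reader might infer from the subgroup plan that the sponsor regards these factors as related to weight loss. A subgroup analysis asks whether the treatment effect differs between groups. That is effect modification, which is distinct from prognosis.
- A reader might call the added precision free. It is not: below a partial R² of about 0.8% the two covariates cost slightly more than they return.
- A reader might expect the overall and subgroup results not to line up. Section 6.3 describes no subgroup model, and separate comparisons within subgroups would fit its wording equally well.

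Two further points are fair. That weight is the sole covariate is read from silence; but if others are intended, the list is open, and it still needs closing before the data are seen. That gender and years of service are held before randomisation is also an inference. It is a safe one for gender, since the pregnancy exclusion in 3.6.7 is applied at pre-screening. For years of service, the planned subgroup analysis needs the value, and length of service at randomisation is not affected by treatment.

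Finally, 6.3 names race alongside the other two. Proposing two of the three without comment would be arbitrary, so race needs an explicit decision.

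**Conclusion.** The point holds as a modest improvement in efficiency and pre-specification. The weight-only model would give a valid answer. Adding gender and years of service risks at most about 0.4 power points and gains about 0.5 to 3.7 points if they explain 2% to 10% of the remaining variance. A gender gap of 2 to 3 points alone is worth about 4 to 10 participants. Protection against imbalance is similarly limited: about a 9% to 12% chance of a gap above 10 percentage points, with a shift near 0.2 points at that threshold under a 2-point outcome gap. The pregnancy withdrawal rule adds some support for gender in particular.

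These sizes rest on assumed alpha, power, R², outcome SD, share of women and gender gap, none of which is in the documents. They show relative effects, not the trial's actual power.

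**What to change.** In section 6.3, before any unblinded analysis, state that the primary model for percentage weight loss contains arm, baseline-visit weight, gender and years of service (continuous), using values as recorded before randomisation, and that this list is complete. State whether race is included, with the reason. Keep the weight-only model as a sensitivity analysis.

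The cost is a sentence or two in 6.3, two degrees of freedom out of 245, and a very small loss of power if the factors prove not to be prognostic. If race is added, it uses one degree of freedom for each category beyond the first. The randomisation and the visit schedule need not change.
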